8.6.1.2 Complete Remission Rate (CRR)

The complete remission rate (CRR), defined as the proportion of subjects who have a CR response according to the IWG criteria using central review. The analysis will consist of the point estimate and 95% 2-sided exact CI, separately by Cohort. Additional analyses will be based on site assessment and by central review using the Lugano (2014) criteria.

8.6.1.3 Progression-Free Survival (PFS)

The non-parametric Kaplan-Meier method will be used to estimate the PFS curve.

Since disease progression is assessed periodically, progressive disease (PD) can occur any time in the time interval between the last assessment where PD was not documented and the assessment when PD is documented. For the primary analysis, for the subjects who have PD, the true date of disease progression will be approximated by the date of the first assessment at which PD is objectively documented per IWG criteria, regardless of discontinuation of study drug. Death is always considered as a confirmed PD event.

A secondary analysis will be performed for PFS based on investigator's assessment.

In order to evaluate the robustness of the PFS endpoint, we will perform two sensitivity analyses with a different set of censoring rules. The first sensitivity analysis is the same as the primary analysis except that it censors at the last disease assessment without PD when PD or death is documented after more than one missed disease assessment. The second sensitivity analysis is the same as the primary analysis except that it considers initiation of new anticancer treatment to be a PD event for subjects without documented PD or death and lost to follow-up to be a PD event for subjects without documented PD or death and lost to follow-up after ≥ 2 missed disease assessments. The censoring rules for primary and sensitivity analyses are summarized in [Table 12](#).

Table 12 Censoring rules for Primary and Sensitivity Analyses of PFS

Situation	Primary Analysis	Sensitivity Analysis 1	Sensitivity Analysis 2
No PD and no death; new anticancer treatment is not initiated	Censored at last disease assessment	Censored at last disease assessment	Censored at last disease assessment
No PD and no death; subject receives SCT following response to pembrolizumab	Censored at last disease assessment before SCT	Censored at last disease assessment before SCT	Censored at date of SCT
No PD and no death; new anticancer treatment is initiated	Censored at last disease assessment before new anticancer treatment	Censored at last disease assessment before new anticancer treatment	Progressed at date of new anticancer treatment
PD or death documented after ≤ 1 missed disease assessment	Progressed at date of documented PD or death	Progressed at date of documented PD or death	Progressed at date of documented PD or death
PD or death documented after ≥ 2 missed disease assessments	Progressed at date of documented PD or death	Censored at last disease assessment prior to the ≥ 2 missed disease assessments	Progressed at date of documented PD or death
No PD and no death and lost to follow-up after ≥ 2 missed disease assessments	Censored at last disease assessment prior to the ≥ 2 missed disease assessments	Censored at last disease assessment prior to the ≥ 2 missed disease assessments	Progressed at date of lost to follow-up.

Similar to the exploratory analysis for ORR above where subjects are treated with MK-3475 by the site following progression, an exploratory analysis will be performed on PFS incorporating additional response assessments; details on this analysis will appear in the sSAP.

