7.1.1.6.3 Subsequent Antineoplastic Therapy Status

The investigator or qualified designee will collect transplant parameters (ie. date and type of transplant, conditioning regimen), and will review all new antineoplastic therapy initiated after the last dose of trial treatment. If a subject initiates a new antineoplastic therapy within 30 days after the last dose of trial treatment, the 30 day Safety Follow-up visit must occur before the first dose of the new therapy. Once new antineoplastic therapy has been initiated the subject will move into survival follow-up.

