7.1.2.6.6 Disease Assessments During the Trial

Disease assessments should be performed per the frequency defined above. There is a \pm 7 day window for assessments performed after Day 1. If PET and CT scan at Screening are negative for disease involvement in the neck, subsequent CT scans may not include neck. If PET and CT scans at Screening are positive for disease involvement of the neck, subsequent CT scans must include neck. Following screening, CT scans should be repeated every 12 weeks for subsequent assessments. PET should be repeated at Week 12, Week 24, to confirm CR or PD and as clinically indicated. Disease assessments and imaging should not be delayed for delays in cycle starts.

Disease assessments and imaging should continue to be performed until documented disease progression, the start of new anti-cancer treatment, withdrawal of consent, death, or the end of the study, whichever occurs first.

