7.1.5.4.2 Survival Follow-up

Once a subject experiences confirmed disease progression or starts a new antineoplastic therapy, the subject moves into the survival follow-up phase and should be contacted approximately every 12 weeks to assess for survival status until death, withdrawal of consent, or the end of the study, whichever occurs first.

CCI

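### Table 12 censors a subject who starts SCT or new anticancer therapy without PD only if no death follows, so PFS censoring depends on a later outcome and fixed-time PFS can shift between yearly updates

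*Combined protocol and SAP*

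**What the plan says.** Section 8.4.1 defines PFS as time from first dose to PD or death from any cause. Table 12 in Section 8.6.1.3 then sets the censoring rules.

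- Two rows cover leaving study therapy without PD: "No PD and no death; subject receives SCT following response to pembrolizumab" and "No PD and no death; new anticancer treatment is initiated". The primary analysis and Sensitivity 1 censor at the last assessment before the SCT or new therapy. Sensitivity 2 censors at the SCT date, or counts an event on the date new therapy starts.
- The rows for PD or death, including "PD or death documented after ≥ 2 missed disease assessments", do not mention earlier SCT or new therapy. The primary analysis and Sensitivity 2 count an event at the PD or death date. Sensitivity 1 does so only after at most one missed assessment.
- The text above the table adds: "Death is always considered as a confirmed PD event".

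Follow-up after a switch is one-sided. Under Section 7.1.2.6.6, imaging runs "until documented disease progression, the start of new anti-cancer treatment" or certain other end points. Deaths are still collected: "Once new antineoplastic therapy has been initiated the subject will move into survival follow-up" (Section 7.1.1.6.3; Section 7.1.5.4.2 agrees).

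Section 8.6.1.5 plans PFS at the primary analysis, at Week 24, at one and two years after the last subject starts, and yearly after that until the trial is complete.

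**The concern.** Kaplan-Meier needs the decision to censor to rest on what is known at that time. Here the same subject is removed before the switch if still alive at the data cut, and kept at risk through an unscanned interval if dead by then. Each update moves newly dead switchers from the first group to the second. That changes the risk sets at all earlier times, including times already fully observed.

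This is not the usual analysis of PFS regardless of later therapy, which would keep surviving switchers at risk too. Table 12 mixes two rules and lets survival choose between them.

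Sensitivity 2 has the fault in sharper form: with new therapy, survivors have their event at the switch and those who die have it later, so dying lengthens PFS. Sensitivity 1 helps only if scans no longer scheduled after a switch count as missed, which Table 12 does not say.

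The situation is foreseen. Section 8.6.3.4 says responders may go on to SCT, and Table 12 gives SCT its own row. Late updates are real as well: results were published in July 2017, and the protocol was still being amended in December 2022, 65 months later. PFS is a key secondary endpoint of a single-arm trial, so the estimate itself is the result.

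**Working it through.** The plan states no PFS rate, landmark time or PFS event count, so there is no figure of its own to reproduce. The check has three parts.

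**1. One subject through Table 12.** Suppose a responder has SCT without PD after the Week 24 scan.

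| Status at data cut | Row that applies | Primary analysis |
|---|---|---|
| Alive | SCT row | Censored at Week 24 |
| Died later | A PD-or-death row | At risk to death, event at death |

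**2. Hand example.** Take 60 subjects: 6 have PD at each of Weeks 12, 24, 36 and 48; 24 are PD-free to Week 96; 12 switch without PD after the Week 24 scan. Let d of the 12 have died by the data cut, all around Weeks 80 to 82.

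PFS at Week 24 is 48/60 = 0.800. At Week 36, 36 + d are at risk and 6 progress; at Week 48, 30 + d are at risk and 6 progress. So

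S(48) = 0.800 × (30 + d)/(36 + d) × (24 + d)/(30 + d) = 0.800 × (24 + d)/(36 + d).

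| d | 0 | 3 | 6 | 12 |
|---|---|---|---|---|
| S(48) | 0.533 | 0.554 | 0.571 | 0.600 |

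Nothing before Week 48 differs between these columns. Censoring all 12 at the switch gives 0.533 throughout; keeping all 12 at risk gives 0.600 throughout.

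**3. Simulation.** The 12-weekly scans come from Section 7.1.2.6.4 and the end of imaging at the switch from Section 7.1.2.6.6. All else is assumed: exponential PD with median 13 months; 5, 15 or 30% of all subjects switching without PD between the first scan and month 24; 20% yearly mortality after the switch, independent of PD risk; 12-month uniform accrual. Deaths before a switch are not modelled separately. Twelve weeks is 84/30.44 = 2.76 months, so the last scan before month 24 is the eighth, at 22.08 months. True 24-month PFS on the scan grid is 0.5^(22.08/13) = 30.8%.

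Primary 24-month PFS (%), by years after the last subject starts:

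| Switching | Year 2 | Year 3 | Year 4 | Year 5 | Time-limited rule, all years |
|---|---|---|---|---|---|
| 5% | 30.5 | 30.8 | 31.1 | 31.3 | 30.8 |
| 15% | 29.6 | 30.8 | 31.6 | 32.2 | 30.8 |
| 30% | 27.8 | 30.6 | 32.5 | 33.9 | 30.8 |

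Two effects compete. Early deaths enter as events without their surviving peers at risk, which pulls the estimate down. Later deaths add time at risk before month 24 without events, which pushes it up.

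- **12-month PFS:** 55.5 to 56.2% (15% switching) and 55.4 to 57.1% (30%), against 0.5^(11.04/13) = 55.5%.
- **Median:** 13.8 months under both rules at every update, except 15.0 against 13.8 at year 5 with 30% switching.
- **Sensitivity 1:** about 0.7 (15%) or 1.6 (30%) points below the time-limited rule at every update if unscheduled scans count as missed; otherwise it equals the primary analysis.
- **Sensitivity 2, half the switches SCT, year 2 to year 5:** 26.6 to 30.6% against 26.4% (15%); 22.1 to 30.7% against 21.6% (30%).
- **Drift within one trial of 60, year 2 to year 5, mean (5th to 95th percentile):** 0.8 (0 to 2.4), 2.6 (0.1 to 5.4) and 6.1 (2.2 to 11.0) points with 5, 15 and 30% switching; exactly 0 under the time-limited rule.
- **Wider grid (median 9, 13 or 18 months; the same switching rates; mortality 10, 20 or 40% per year):** the drift in 24-month PFS is upward in all 27 cells, by 0.4 to 7.9 points.

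**The case against.** The strongest objection is that no row names death after a switch. The censoring dates are set before the switch, so the row labels could describe status at that moment, and a programmer might censor anyway. The DOR rule in Section 8.6.1.4, which lists antitumor treatment including SCT as a reason to censor, hints at that intent. But the sentence that death always counts points the other way. If censoring is intended, the text still needs correcting. DOR is itself unclear, because it does not say which rule wins when death follows that treatment.

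A clarification may also sit in the supplemental SAP, which was not among the documents. Sections 8.6.1.3 and 8.6.1.4 send only exploratory analyses there, but Section 8.0 lets it hold changes to non-confirmatory analyses, and PFS has no hypothesis. That possibility stands.

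On size, the median seldom moves. At 15% switching, 24-month PFS is off by at most 1.4 points against a standard error of about 6 (√(0.308 × 0.692/60) = 0.060). If all switchers are responders at the 69% ORR in Section 4.3, 30% switching means 0.30/0.69 = 43% of responders. These points limit the weight of the concern. The standard error is not the yardstick for the drift, though, because the drift occurs within the same subjects.

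The death from acute graft-versus-host disease in Section 4.3 is weak support. The documents do not say whether it followed an on-study transplant or whether PD came first, and subjects with an allogeneic transplant more than five years earlier could enrol.

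Finally, following every switcher to death would also remove the drift. But imaging stops at the switch, so PD would go unseen in that interval. Censoring extends what Table 12 already does for surviving switchers.

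**Conclusion.** The concern holds. Followed as written, Table 12 makes PFS censoring depend on whether the subject later dies, in the primary analysis and Sensitivity 2, and in Sensitivity 1 to an extent the plan leaves undefined. Fixed-time PFS can then move between updates with no earlier data changed.

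The mechanism follows from the text alone. The size rests on assumed switching and death rates: in the central case, mean drift in 24-month PFS from year 2 to year 5 at n = 60 is under 1 point with 5% switching, 2.6 points with 15% and 6.1 points with 30%. The 12-month estimate and the median are much less affected. For DOR the finding is ambiguity only. The ORR test is untouched.

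This should be corrected, but it does not threaten the trial's main conclusion. Confidence is medium because the supplemental SAP was not available and the post-allogeneic follow-up text (Section 7.1.5.4.1) is redacted.

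**What to change.** In Table 12, make the SCT and new-therapy rows apply to subjects with no PD or death before the switch, and limit the PD-or-death rows to events before any switch. Qualify the sentence on death to match. Primary and Sensitivity 1 then censor every switcher at the last assessment before the switch. Sensitivity 2 counts every new-therapy start as an event on its date and censors every post-response SCT at the SCT date, whatever follows.

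Rewording alone leaves overlaps, so also state that:

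1. the SCT row takes precedence over the new-therapy row for a post-response SCT and its conditioning, since both could match;
2. the row "No PD and no death and lost to follow-up after ≥ 2 missed disease assessments" takes precedence over the first row, since both can match and Sensitivity 2 treats them differently;
3. assessments no longer scheduled after a switch are not missed.

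In Section 8.6.1.4, say that DOR is censored at the last assessment before antitumor treatment or SCT even if death follows. Keep PFS regardless of later therapy, with all switchers treated alike, as a sensitivity analysis for comparability with earlier updates. If the supplemental SAP already holds such a rule, cross-reference it in Table 12.

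The cost is wording and re-derivation of PFS and DOR dates from data already collected. A few late deaths leave the PFS event count but remain in OS. Earlier reported PFS must be re-derived and the change labelled as made after results were known.

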8.6.1.4 Duration of Response (DOR)

Duration of response is defined, only for the subgroup of subjects who achieve CR or PR, as the time from start of the first documentation of objective tumor response (CR or PR) to the first documentation of tumor progression or to death due to any cause, whichever comes first. The analysis will consist of Kaplan-Meier estimates. Duration of response data will be censored on the date of the last disease assessment documenting absence of progressive disease for subjects who do not have tumor progression and are still on study at the time of an analysis, are given antitumor treatment (including stem cell transplant) other than the study treatment, or are removed from study prior to documentation of tumor progression.

Duration of Response will be based upon central review according to the IWG criteria; a secondary analysis of DOR will be conducted using investigator assessment. In addition, since stem cell transplant post-initiation of MK-3475 is considered to be an indicator of positive efficacy rather than failure of the current treatment, an exploratory analysis of DOR may be conducted where date of SCT is not considered censored for those subjects; details will appear in the sSAP.

8.6.1.5 Overall Survival (OS)

The median overall survival, if reached, will be estimated in the given analysis population, separately by cohort. In addition, the Kaplan-Meier method will be used to estimate the survival curve, separately by Cohort.

Table 13 Efficacy Analysis Methods for Primary and Secondary Efficacy Endpoints

Endpoint/Variable	Statistical Method	Analysis Population	Missing Data Approach
Primary:			
Overall Response Rate 
 • IWG criteria (2007) 
 ◦ Central review 	Exact test of binomial parameter; 2-sided 95% exact CI	ASaT/FAS	Subjects with missing data are considered non-responders
Secondary:			
Overall Response Rate 
 • IWG criteria (2007) 
 ◦ Study site • Lugano criteria (2014) 
 ◦ Central review 	Point estimate; 2-sided 95% exact CI	ASaT/FAS	Subjects with missing data are considered non-responders
Complete Remission Rate 
 • IWG criteria (2007) 
 ◦ Central review ◦ Study site • Lugano criteria (2014) 
 ◦ Central review 	Point estimate; 2-sided 95% exact CI	ASaT/FAS	Subjects with missing data are considered non-responders
Progression-free survival 
 • IWG criteria (2007) 
 ◦ Central review ◦ Study site 	Summary statistics using Kaplan-Meier method	ASaT/FAS	Censored at last assessment (see Table 12 for sensitivity analyses based on alternative censoring)
Duration of Response 
 • IWG criteria (2007) 
 ◦ Central review ◦ Study site 	Summary statistics using Kaplan-Meier method	All responders	Non-responders are excluded in analysis
Overall survival	Summary statistics using Kaplan-Meier method	ASaT/FAS	Censored at last assessment

As indicated in Section 8.6.1.1, the primary analysis of ORR will be conducted when the last treated subject has reached the Week 12 response assessment or has discontinued study therapy. At that time point, analyses of other efficacy endpoints in the table above (eg, DOR, CRR, PFS and OS) will also be conducted. An efficacy update for all endpoints in the table above will be conducted when the last treated subject has reached at least the Week 24 response assessment or has discontinued study therapy. An efficacy update will be conducted at one year after the last subject initiated treatment and then at 2 years after the last subject initiated treatment, which corresponds to the end of the protocol-specified treatment period. Subsequent yearly analyses will be conducted (ie, 3 years after the last subject initiated treatment, etc.) until the trial is complete, including follow-up information on subjects who enter the re-treatment period.

8.6.2 Statistical Methods for Safety Analyses

Safety and tolerability will be assessed by clinical review of all relevant parameters including adverse experiences (AEs), laboratory tests, vital signs, and ECG measurements.

Summary statistics (counts, percentage, mean, standard deviation, etc.) will be provided for the safety endpoints as appropriate.

8.6.3 Summaries of Baseline Characteristics, Demographics, and Other Analyses

8.6.3.1 Baseline Characteristics and Demographics

Baseline characteristics will be assessed by the use of tables and/or graphs for each Cohort. No statistical hypothesis tests will be performed on these characteristics. The number and percentage of subjects screened, allocated, the primary reasons for screening failure, and the primary reason for discontinuation will be displayed. Demographic variables (eg, age, gender), baseline characteristics, primary and secondary diagnoses, and prior and concomitant therapies will be summarized by cohort either by descriptive statistics or categorical tables.

8.6.3.2 Patient-reported Outcomes (PRO)

EORTC QLQ-C30 and EuroQoL EQ-5D data will be summarized as part of the pre-specified exploratory analysis. Patient-reported treatment effects will be evaluated for each cohort separately at pre-specified time points while on treatment and 30 days following treatment discontinuation as measured by change from baseline in the QLQ-C30 QoL domain and all sub-scales/single items. In addition to the estimated mean effects, cumulative distribution and the number and proportion of patients who “improved,” “worsened,” or “remained stable” from baseline to a pre-defined visit will also be estimated. For EQ-5D, pre-specified exploratory analyses will be performed to describe the distribution of responses. Additional details will be included in the sSAP.

8.6.3.3 Population PK Analyses

Based on pharmacokinetic data obtained within this study, a separate population Pharmacokinetics (PK) analysis will be performed. The prospective details of this analysis will be specified in a separate population PK analysis plan.

8.6.3.4 Other Analyses

Subjects that respond to study therapy (CR/PR) in this study may now be considered for SCT (autologous for prior ineligible subjects, allogenic for previous transplant failure subjects). The number of subjects that become eligible for SCT post study therapy and the number of subjects that actually receive SCT post study therapy will be estimated using descriptive statistics, separately by cohort.

Descriptive statistics, including cross-tabulations, will be performed for those patients with evaluable samples, to assess PD-L1 expression using immunohistochemistry will be analyzed in the context of response determined by central review (CR, PR, SD, PD).

Additional exploratory analyses will be described in the sSAP.

8.7 Interim Analysis

An interim analysis will be performed within each cohort for the purpose of futility alone. The analysis will be performed and reviewed by the study team. In each cohort separately, the analysis will be performed based on response assessed by the investigators for 30 subjects. The analysis will be conducted when the 30th subject who starts study treatment for that cohort has reached the Week 12 response assessment or has discontinued study therapy prior to Week 12, ie, all 30 subjects will have been evaluated for response with at least the Week 12 response assessment or have discontinued prior to Week 12.

Enrollment into each cohort will not be paused pending the results of the analysis.

For Cohorts 1 2 and 3, if 6 or fewer responses (CR or PR at any assessment) out of 30 subjects are observed (20%), the cohort may be stopped for further enrollment. The operating characteristics of the futility stopping rule are given in [Table 14](#) below, ie, the probability of potentially stopping a cohort under the rule for a range of true ORR for MK-3475.

Table 14 Operating Characteristics of Interim Analysis Rule

True ORR	Probability of Stopping Enrollment
	Cohorts 1, 2 and 3 (if observe $\leq 6/30$ [20%])
5%	>0.99
10%	0.97
15%	0.85
20%	0.61
25%	0.35
30%	0.16
35%	0.06
40%	0.02
45%	<0.01

8.8 Sample Size and Power Calculation

Efficacy for each cohort will be analyzed separately.

The proposed sample size for each of the three cohorts is 60 subjects in the primary analysis population (ASaT), i.e. 180 subjects in all. To obtain 180 total subjects in the ASaT population, 190 will need to be enrolled in the study assuming that approximately 5% of enrolled subjects are not treated.

With 60 subjects per cohort in the primary analysis population, there is at least 93% statistical power (1-sided nominal 2.5% alpha) to detect a 40% or higher overall response rate (ORR) for the MK-3475 arm compared to a fixed control rate of 20% using the exact binomial test (nQuery version 2.0 software). Success for this hypothesis requires at least 16/60 responses. If an interim analysis is performed within a cohort (see Section 8.7), the power will be approximately 92%.

The selection of 20% as a fixed control rate is based partly on historical data in previously conducted studies in R/R HL prior to the approval of brentuximab vedotin, where response rates ranged between 18%-53% (Johnston et al, 2010, Feninger et al, 2011, Younes et al, 2012, and Moscowitz et al, 2012). However, since this study is being conducted in brentuximab vedotin failures and to date, there is no published data on the ORR in this particular patient population. Thus, a 20% ORR may be taken as a conservative control rate considering that all subjects to be enrolled in this study have failed an additional line of therapy (brentuximab vedotin) than seen previously.

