3.0 OBJECTIVE(S) & HYPOTHESIS(ES)

3.1 Primary Objective(s) & Hypothesis(es)

Within each of, and pooled over, the 3 specified cohorts defined in Section 5.1.2. for subjects with relapsed/refractory (R/R) classical Hodgkin lymphoma (cHL):

(1) **Objective:** To determine the safety and tolerability of pembrolizumab.

Within each of the 3 cohorts of subjects with R/R cHL:

(2) **Objective:** To evaluate the Overall Response Rate (ORR) of pembrolizumab by independent central review according to the International Working Group (IWG) response criteria (Cheson, 2007).

Hypothesis: Intravenous administration of single agent pembrolizumab will result in an ORR of greater than 20% in each of the three cohorts using IWG response criteria (Cheson, 2007) by independent central review.

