observed were Grade 1 and 2, which resolved with appropriate clinical management. No Grade 4-5 drug related adverse events (DRAEs) were reported, but two patients discontinued therapy due to a DRAE: Grade 2 pneumonitis, and Grade 3 nephrotic syndrome [47]. The present study, KEYNOTE-087 (ClinicalTrials.gov, NCT02453594), is a multicenter, single-arm, multicohort phase 2 study of pembrolizumab in 3 cohorts of patients. Among 210 treated patients in cohorts 1 (n = 69), 2 (n = 81), and 3 (n = 60), all patients had refractory disease or relapsed HL. Per blinded independent central review, the ORR was 69.0% (95% CI, 62.3% to 75.2%), and the CRR was 22.4% (95% CI, 16.9% to 28.6%). By cohort, ORRs were 73.9% for cohort 1, 64.2% for cohort 2, and 70.0% for cohort 3. Thirty-one patients had a response \geq 6 months. With a median of 13 treatment cycles, the most common treatment-related AEs (TRAEs) were hypothyroidism (12.4%) and pyrexia (10.5%). The most common grade 3/4 TRAEs were neutropenia (2.4%), dyspnea (1%), and diarrhea (1%). Immune-mediated AEs (events with potentially drug-related immunologic causes regardless of treatment attribution) and infusion-related reactions were reported in 60 patients (28.6%), most commonly hypothyroidism (13.8%). Nine patients (4.3%) discontinued because of TRAEs (myocarditis, myelitis, myositis, pneumonitis, infusion-related reactions, cytokine release syndrome), and 26 patients (12.4%) experienced TRAEs resulting in treatment interruptions. Two patients died during follow-up as a result of septic shock and acute graft-versus-host disease, respectively; neither of these deaths were considered to be treatment related [48]. Taken together, the observed efficacy and safety data indicate that MK-3475 has the potential to alter the disease course in these RRHL patients and potentially prolong patient survival.

In conclusion, pembrolizumab demonstrates a very promising anti-cancer activity in relapsed or refractory Hodgkin Lymphoma patients with an acceptable safety profile compared to those of existing therapeutic options. On-going and planned studies will allow for a more comprehensive analysis of benefit/risk balance of pembrolizumab.

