8.9 Multiplicity

The false positive rate for testing the primary efficacy endpoint is controlled at 0.025 (1-sided) within each cohort. No additional multiplicity adjustment is required because each

cohort will be evaluated independently and only once, i.e. at the time of the primary analysis when all subjects in the cohort have reached the week 12 assessment or have discontinued study therapy.

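### The stated success threshold of 16/60 responses gives a one-sided type I error of 13.1% per cohort, not 2.5%; the planned exact test needs 19/60

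*Combined protocol and SAP*

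**What the plan says.** Section 3.1 gives the primary efficacy hypothesis: treatment "will result in an ORR of greater than 20% in each of the three cohorts", by independent central review. Section 8.3 makes this the only formally tested hypothesis, tested separately in each cohort.

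Section 8.8 supplies the design figures. On size: "The proposed sample size for each of the three cohorts is 60 subjects in the primary analysis population (ASaT"). On power: "there is at least 93% statistical power (1-sided nominal 2.5% alpha") for a true ORR of 40% or more, "compared to a fixed control rate of 20% using the exact binomial test". Power falls to about 92% if the interim analysis is done. The decision count follows: "Success for this hypothesis requires at least 16/60 responses".

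Section 8.6.1.1 plans the exact binomial test together with a two-sided 95% Clopper-Pearson interval. Section 8.9 makes the error claim: "The false positive rate for testing the primary efficacy endpoint is controlled at 0.025 (1-sided) within each cohort". Table 11 repeats the sample size, alpha, rates and power but gives no response count. Nothing else in the document supports 16/60 or gives a different count.

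**The concern.** Once n, the null rate, alpha and the test are fixed, the critical count follows and cannot be chosen freely. A count of 16/60 is an observed rate of 26.7%, only 6.7 percentage points above the null. With 60 subjects that looked too small a margin for an exact test at one-sided 2.5%.

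At stake is the success criterion for the only tested hypothesis, in all three cohorts. If the sentence is applied as written, the error control claimed in Section 8.9 is lost. If the exact test is applied instead, the sentence is false. For 16 to 18 responses the two rules give opposite answers, and the plan does not say which governs.

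**Working it through.** **Inputs.** From Section 8.8: n = 60, null rate 0.20, alternative 0.40, one-sided alpha 0.025, exact binomial test, stated threshold 16. From Section 8.7: enrollment may stop if 6 or fewer of the first 30 subjects respond. From Section 4.3: treated numbers 69, 81 and 60.

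**Step 1: error and power for each candidate threshold.** With X ~ Binomial(60, p), type I error is P(X ≥ r | p = 0.20) and power is P(X ≥ r | p = 0.40). The lower Clopper-Pearson limit is the rate at which P(X ≥ r) = 0.025, so it lies above 20% exactly when the one-sided exact p-value is below 0.025.

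| r | Type I error at 20% | Power at 40% | Lower 95% Clopper-Pearson limit |
|---|---|---|---|
| 16 | 0.1306 | 0.9891 | 0.1607 |
| 17 | 0.0772 | 0.9779 | 0.1745 |
| 18 | 0.0427 | 0.9587 | 0.1885 |
| 19 | 0.0221 | 0.9281 | 0.2026 |

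The smallest r with type I error at or below 0.025 is 19. The full interval is 16.1% to 39.7% at 16/60 and 20.3% to 45.0% at 19/60.

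**Step 2: reproduce the plan's power.** With r = 19, power is 92.8%, against the stated 93% (a rounding difference). With the futility rule applied,

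P(success) = Σ (x = 7 to 30) b(x; 30, p) · P(Y ≥ r − x), where b is the binomial probability and Y ~ Binomial(30, p).

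This treats interim and final responses as the same reading and the rule as binding.

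| r | Type I error at 20%, with futility | Power at 40%, with futility |
|---|---|---|
| 16 | 0.1137 | 0.9758 |
| 19 | 0.0213 | 0.9218 |

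The stated figure of about 92% matches r = 19. With r = 16 neither stated power is reproduced. The Table 14 stopping probabilities also reproduce (for example 0.607 at 20% and 0.017 at 40%), so the futility rule was read correctly.

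**Step 3: could another test or alpha give 16?** One-sided p-values at 16/60 are 0.098 (z test with null variance), 0.129 (continuity-corrected), 0.122 (Wald) and 0.104 (mid-p). None approaches 0.025. With the exact test, one-sided alpha of 5% needs 18 and 10% needs 17. At n = 60, 16 is the exact critical count for a null rate of 15% (type I error 0.0136). It may be left over from a different null, but that is inference and the documents do not say so.

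**Step 4: size of the discrepancy.** The ratio to nominal alpha is 0.1306 / 0.025 = 5.2. A cohort with true ORR of 20% lands on 16 to 18 responses with probability 0.1306 − 0.0221 = 0.1085, about 10.9%. Over three independent cohorts all at 20%, the chance of at least one false success is 1 − (1 − 0.1306)³ = 0.343 with 16, and 1 − (1 − 0.0221)³ = 0.065 with 19.

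**Step 5: the cohort sizes actually treated.** Section 4.3 reports: "Among 210 treated patients in cohorts 1 (n = 69), 2 (n = 81), and 3 (n = 60"). The exact critical counts are 22/69 (type I error 0.0134), 25/81 (0.0135) and 19/60 (0.0221). A count out of 60 does not fit the first two cohorts.

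**The case against.** The strongest reply is that 13.1% is conditional. Sections 8.6.1.1 and 8.9, Table 11 and Table 13 define the analysis through the exact test or its alpha, without mentioning 16/60. If that test decides, type I error at n = 60 is 2.2% and the faulty sentence does no harm. The trial is also not mis-sized: n, alpha, both power figures and the futility rule agree with one another and with 19. The three-cohort figure of 34% concerns familywise error, which the plan does not claim to control, and even the correct threshold gives 6.5%. Treating the futility rule as binding lowers 13.1% to 11.4%. Finally, Section 4.3 reports central-review ORRs of 73.9%, 64.2% and 70.0%, far above 16/60 (26.7%) and above all three exact critical counts (22/69 = 31.9%, 25/81 = 30.9%, 19/60 = 31.7%), so the choice of threshold does not alter the reported result.

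Most of this stands as qualification. The error is confined to one number, the 34% is secondary, and the reported conclusion is unaffected. It does not rescue the sentence. Section 8.8 states what success requires, and a reader would naturally take the count as the critical value. It contradicts the test named in the same paragraph, and no text gives either one precedence. Even with binding futility the error is more than four times nominal (0.1137 / 0.025 = 4.5), and Section 8.7 only says that a cohort may be stopped.

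**Conclusion.** The concern holds. The threshold of 16/60 is wrong as written; the exact one-sided 2.5% critical count for n = 60 against 20% is 19. Used as the decision rule, 16/60 carries a type I error of 13.1% per cohort (11.4% if the futility rule is binding) instead of at most 2.5%. If the exact test governs, the error is 2.2% and the sentence is simply incorrect.

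This rests only on the plan's own n, null rate, alpha and test, with independent binomial responses; the with-futility figures also rest on the simplifications in the working. The agreement of both stated powers with 19 shows that the threshold, and not the alpha or the sample size, is the faulty figure. Because it is the success rule for the only tested hypothesis, it must be corrected even though the reported response rates exceed either value.

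**What to change.** In Section 8.8, replace 16/60 with 19/60. Also define success by the test and not by a fixed count: exact one-sided p ≤ 0.025 against 20%, equivalently a lower two-sided 95% Clopper-Pearson limit above 20%, at the actual ASaT size of each cohort. For the treated numbers in Section 4.3, give the resulting counts of 22/69, 25/81 and 19/60.

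The text change is one or two sentences. The stated threshold becomes stricter; sample size, power, futility rule, data collection and procedures stay as they are. Section 8.0 requires a protocol amendment for changes to primary-hypothesis methods before final database lock, so the correction should go through that route, or be recorded as an erratum in the clinical study report if lock has passed. Either record should note that the results already reported clear both thresholds.
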